#### 7. SURGICAL PROCEDURES

None

#### 8. PRECAUTIONS & WARNINGS FOR ENSURING PATIENT SAFETY

In the physical therapy unit, there will be an emergency kit and healthcare personnel ready for intervention in terms of possible complications (hypotension, emergency cardiological conditions, skin reactions, burns, etc.) that may develop during treatment. During the application, the practitioner and the patient will have protective

Protocol name/ version number /date: Efficacy of high-intensity laser therapy in patients with partial supraspinatus tears Versivon no: 02 -Tarih: 02.12.2020

glasses.

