#### SECONDARY PURPOSE

Comparison of two different applications of high-intensity laser with 5 sessions and 10 sessions in terms of

Protocol name/ version number /date: Efficacy of high-intensity laser therapy in patients with partial supraspinatus tears Versiyon no: 02 - Tarih: 02.12.2020

effectiveness in patients with partial supraspinatus tear

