**Exclusion Criteria and Practices in this Case** 

Patients will be excluded from the study if they do not attend follow-up and laser sessions regularly.

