## 5. STUDY DESIGN & METHOD

#### STUDY DESIGN

90 patients aged 20-60 years who were diagnosed with partial supraspinatus tear and met the inclusion criteria of the study will be included in the study. Patients will be randomized into three groups: 30 patients in the first group who have 5 sessions of high-intensity laser, 30 patients in the second group who have 10 sessions of high-intensity laser, and 30 patients in the third group control group who have only exercises. It was planned to give 5 sessions of laser+exercise every other day to the the first group, 10 sessions of laser+exercise every other day to the second group, and only exercise program three days in a week to the control group. All groups will be evaluated with joint range of motion (ROM) (measurements including abduction, adduction, flexion, extension, internal and external rotation by goniometer according to neutral 0 position), visual analog scale (VAS), shoulder pain dissability index, quickdash, constant score at 0th month, 1st month, 3rd and 6th months.

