6. COLLECTION OF STUDY DATA

#### Data Recording/ Case Report Forms

A Case Report Form will be completed for each registered patient and signed by the responsible investigator or an authorized representative of the study staff. This also applies to enrollments for patients who did not complete the study (even during pre-randomisation screening, if a case report form was prepared). If a patient withdraws from the study, the reason for this will be recorded on the Case report form. If a patient is withdrawn from the study due to a treatment-limiting adverse event, every effort will be made to clearly document the outcome. All forms must be typewritten or filled with indelible ink and be legible. Errors can be crossed out, but errors cannot be erased; correction is entered and the change is initialed and dated by the researcher or his authorized representative. The investigator will ensure that the data reported to the sponsor in case report forms and all required reports are correct, complete, legible and processed in a timely manner. The researcher is responsible for the accuracy of the data transferred on the forms and will sign these forms to show their compatibility with the recorded data.

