### 9. CONDITIONS TO STOP THE STUDY

There is an unresolved malfunction in the device in the protocol

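### Burns and skin reactions are named as possible, but adverse events that do not lead to withdrawal have no stated route into the data or the report

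*Combined protocol and SAP*

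**What the plan says.** Section 8 (Precautions & Warnings) refers to "possible complications (hypotension, emergency cardiological conditions, skin reactions, burns, etc.) that may develop during treatment". It does so to explain why an emergency kit and staff will be at hand, and it does not say that such events will be recorded.

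The term adverse event occurs once, in section 6 under Data Recording/Case Report Forms: "If a patient is withdrawn from the study due to a treatment-limiting adverse event, every effort will be made to clearly document the outcome". The same paragraph says "A Case Report Form will be completed for each registered patient", extends this to patients who do not finish, and adds "If a patient withdraws from the study, the reason for this will be recorded on the Case report form". It does not list the form's fields.

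Study Design (section 5) lists goniometer range of motion, a pain scale, and "shoulder pain dissability index, quickdash, constant score at 0th month, 1st month, 3rd and 6th months". All are efficacy measures. Statistical & Analytical Methods (section 10) describes ANOVA, split-mixed ANOVA and post-hoc tests, with no safety summary.

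Three other places bear on the point:

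- Section 4, Exclusion Criteria and Practices in this Case: "Patients will be excluded from the study if they do not attend follow-up and laser sessions regularly". No exception is made for absence caused by an adverse event.
- Secondary Purpose: "Comparison of two different applications of high-intensity laser with 5 sessions and 10 sessions". The sentence goes on to limit this comparison to effectiveness.
- Section 9 gives a single condition for stopping the study: "There is an unresolved malfunction in the device in the protocol".

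**The concern.** The protocol foresees thermal and skin injury and prepares to respond to it, but it does not say how such injury becomes data unless the patient leaves the study. A minor burn in a patient who carries on is the kind of event most likely to be missed, and it is hard to reconstruct once the session is over.

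Two laser courses are being compared, one with twice the planned sessions of the other. A reader of the results will want to know what the longer course cost patients as well as what it gained. A report with no event counts could be taken as evidence of no harm when it shows only that nobody was required to ask. The attendance rule adds to this: a patient who stops coming after a skin reaction may be excluded for irregular attendance, and nothing says that such a patient will appear in any safety summary.

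**Working it through.** **The plan's own figure.** The plan gives no number for harm. Its one sample-size figure concerns efficacy. For a one-way ANOVA with 3 groups, f = 0.40, alpha 5% and power 90%, the noncentral F calculation (noncentrality f²N) gives a smallest N of 83, or 84 in equal groups. Power is 0.907 at 84 and 0.926 at 90. The stated 84 is reproduced, and it has no bearing on harm.

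**Where each kind of event goes under the text**

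| Event | Stated recording | Stated analysis |
|---|---|---|
| Treatment-limiting, patient withdrawn | Reason for withdrawal and outcome (section 6) | None |
| Patient stops attending after an event | Form kept for non-completers; reason recorded if this counts as a withdrawal (section 6); may be excluded (section 4) | None |
| Not treatment-limiting, patient continues | None stated | None |

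The third row is the gap in collection. The last column is the gap in reporting.

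**Planned exposure** (30 per arm, Study Design): 30 × 5 = 150 laser sessions and 30 × 10 = 300 laser sessions.

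**Would there be anything to record?** The documents give no event rate, so a range is assumed. The chance of at least one affected patient among 30 is 1 − (1 − p)^30:

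- p = 2%: 0.45
- p = 5%: 0.79
- p = 10%: 0.96

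**What full recording would give.** With zero events in n patients, the one-sided 95% upper bound is 1 − 0.05^(1/n):

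- n = 30 (one arm): 9.5%; the two-sided exact limit, 1 − 0.025^(1/30), is 11.6%
- n = 28 (84/3, after the allowed losses): 10.1%
- n = 60 (both laser arms pooled): 4.9%

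**What it would not give.** With Fisher's exact test at 5% and 30 per arm, a comparison against 0/30 needs at least 6/30 (p = 0.024; 5/30 gives p = 0.052). Exact power under assumed rates is:

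- 10% v 5%: 0.02
- 20% v 10%: 0.10
- 20% v 0%: 0.57
- 30% v 0%: 0.92

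Arm-level counts would be informative as description. A formal harm comparison between 5 and 10 sessions would not be.

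**Would common visits cover treatment?** At one session every other day, 5 sessions span 9 days and 10 sessions span 19 days. If months are counted from the start of treatment, which the protocol does not state, both laser courses end before the month 1 visit. A question at that visit then covers the whole course in both laser arms.

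**The case against.** The strongest reply is that much of this is read from silence. The Case Report Form is not among the documents and may already hold an adverse-event field. Section 6 places an extra duty on treatment-limiting events; it does not say that others go unrecorded. Section 8 speaks of possible complications, which is weaker than expecting them. All of this stands, and it limits the point to what the protocol requires. It does not close the gap: no text asks for non-limiting events, and no analysis would use them.

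Three stronger readings are tempting and are not supported.

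- A reader might infer that patients with treatment-limiting events vanish from the data. Section 6 keeps a form for non-completers, records why a patient withdrew and documents the outcome of a limiting event. Such withdrawals could be counted by arm, although no such count is planned.
- A reader might infer that the trial promises a benefit-harm comparison of 5 and 10 sessions and fails to deliver it. Secondary Purpose promises effectiveness only.
- A reader might infer that better recording would allow the arms to be tested for harm. At 30 per arm the power figures rule that out for plausible differences.

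A further objection is that asking at every session gives the arms 5, 10 or a different number of occasions to report, in a trial with no blinding. More events in the 10-session arm could then reflect more asking. This stands, and it shapes the fix.

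**Conclusion.** The point holds as a gap in collection and reporting. Non-limiting adverse events have no stated route into the data, and no adverse event of any kind has a stated place in the analysis. The efficacy objectives and the sample size are unaffected. What is lost is any usable account of harm beside the efficacy result, over a planned 450 laser sessions (150 + 300).

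The size cannot be fixed from the documents because they give no event rate. Under assumed risks of 2% to 10% per patient, the chance that an arm of 30 has at least one affected patient runs from 45% to 96%. Even complete recording would support description only, with an upper bound of 9.5% when no events are seen in an arm.

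The conclusion assumes that no adverse-event field or safety summary is required in a study document outside the protocol. If the form already has such a field, the remaining change is to say so and to add the table. The change is worth making because it is cheap and the information is hard to recover afterwards.

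**What to change.** In section 6, require an adverse-event entry on the existing Case Report Form for every patient. It should cover the complications named in section 8 and any other event, and be asked in the same words at months 1, 3 and 6 in all three arms. Immediate reactions should also be noted at each session.

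In section 10, add one table: the number and percentage of patients with at least one event by arm, with exact confidence intervals, among all randomised patients, including those excluded for irregular attendance. Label it descriptive. Base the between-arm comparison on the common visits, and report session-level events separately, because the three schedules give unequal chances to report.

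The cost is one form entry, one table and minor recording work. Two limits remain and should be stated in the report: session-level ascertainment stays unequal between arms, and reporting is unblinded throughout. No treatment, schedule or efficacy analysis changes.

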### 9. CONDITIONS TO STOP THE STUDY

There is an unresolved malfunction in the device in the protocol

## **10. STATISTICAL PROCEDURES**

Sample Size

Sample size calculation was made using G\*POWER 3.1.9 program. Using the findings of a similar study conducted before (6), it was predicted that a high level of effect size would be obtained between the groups (f=0.40) for the SPADI score of  $22\pm1.2$  for the 6th month before and after the treatment and  $41.4\pm2.6$  for the control group (f=0.40), 90% power, and type 1 error level: 5%, it is aimed to reach at least 84 people in total, and at least 90 people considering that there may be losses in the follow-up.

#### Statistical & Analytical Methods

The data will be analyzed with the SPSS 18.0 package program. GraphPad for Windows will be used in the randomization process. Continuous variables will be presented as mean and standard deviation or median (25p-75p). Categorical variables will be presented as percentages. The conformity of the data to the normal distribution will be evaluated with the Shapiro Wilk test. Analysis of variance (ANOVA) and split-mixed ANOVA will be used in the analysis of within-group changes and in repeated measures of significance between the differences between groups. Tukey and Games Howell tests will be used in post-hoc tests.

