# PRİMARY PURPOSE

Demonstrating the efficacy of high-intensity laser therapy in patients with partial supraspinatus tears

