## **3. HYPOTHESIS OF THE STUDY**

H0: High-intensity laser therapy is ineffective in patients with partial supraspinatus tears.

H1: High-intensity laser therapy is effective in patients with partial supraspinatus tears.

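### SPADI at month 6 carries the sample size, but the plan never designates it, or any one test, as the result that decides H1

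*Combined protocol and SAP*

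**What the plan says.** The primary purpose is "Demonstrating the efficacy of high-intensity laser therapy in patients with partial supraspinatus tears". The hypothesis section states "H1: High-intensity laser therapy is effective in patients with partial supraspinatus tears". Neither names an outcome, a visit or a contrast between groups. The secondary purpose, comparing 5 with 10 sessions, ranks the questions but not the outcomes.

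The Study Design section lists the outcomes with equal standing: range of motion ("measurements including abduction, adduction, flexion, extension, internal and external rotation by goniometer according to neutral 0 position"), then "visual analog scale (VAS), shoulder pain dissability index, quickdash, constant score at 0th month, 1st month, 3rd and 6th months". That makes four scales and six directions, at baseline and three follow-up visits.

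SPADI at month 6 is singled out only under Sample Size, where "it was predicted that a high level of effect size would be obtained between the groups (f=0.40) for the SPADI score of" is followed by "90% power, and type 1 error level: 5%, it is aimed to reach at least 84 people in total". The word primary is not used there.

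Under Statistical & Analytical Methods, "Analysis of variance (ANOVA) and split-mixed ANOVA will be used in the analysis of within-group changes and in repeated measures of significance" gives the tests, and "Tukey and Games Howell tests will be used in post-hoc tests" gives the only multiplicity device. That section names no outcome, no visit and no model term (group, time or interaction) as decisive.

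**The concern.** A sizing assumption says what the trial was planned to detect. It does not bind the analysis. As written, the investigators could see the data and then rest H1 on VAS, abduction or the Constant score, or on a time effect rather than a group effect, without departing from the plan. The 5% in the sample-size paragraph would then not describe the error of the efficacy claim. Tukey and Games-Howell do not help here, because they adjust for the three group pairs within one outcome and not across outcomes or visits. The trial is unblinded, which makes it more important to fix the deciding result beforehand.

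There is a related gap. The 90% power belongs to a test of whether the three groups differ at all, whereas the primary purpose is answered by comparing laser with control.

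**Working it through.** **Step 1. Reproduce the plan's figure.** Inputs from the Sample Size paragraph: f = 0.40, 5% error, 90% power; three equal groups from Study Design. For a one-way ANOVA F test the noncentrality is λ = N × f².

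- N = 84: λ = 84 × 0.16 = 13.44, df 2 and 81, power 90.7%.
- N = 81: power 89.5%.
- N = 90: power 92.6%.

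So 84 is the smallest equal-group total that reaches 90%. The whole 5% goes to one three-group test of one outcome.

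**Step 2. Error rates if any outcome may carry the claim.** If the tests were independent, the chance of at least one false positive would be 1 − 0.95⁴ = 18.5% for four scales and 1 − 0.95¹⁰ = 40.1% for ten outcomes. The outcomes will be correlated, and the documents give no correlations, so a range is assumed. Simulation: three groups of 28, no true differences, equally correlated normal outcomes, one-way ANOVA at 5% on each at a single visit, 20,000 runs.

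At least one false three-group difference of any kind:

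| Outcomes | ρ = 0.3 | 0.5 | 0.7 | 0.9 |
|---|---|---|---|---|
| One | 5% | 5% | 5% | 5% |
| Four scales | 17.4% | 16.1% | 13.4% | 9.5% |
| Ten outcomes | 36.0% | 30.2% | 22.2% | 13.4% |

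At least one false finding that laser is better than control (significant F, and at least one laser arm better than control by Tukey):

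| Outcomes | ρ = 0.3 | 0.5 | 0.7 | 0.9 |
|---|---|---|---|---|
| One | about 1.7% | 1.7% | 1.7% | 1.7% |
| Four scales | 6.1% | 5.2% | 4.8% | 3.3% |
| Ten outcomes | 12.7% | 10.4% | 8.3% | 4.8% |

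The second table is the one that matches H1. Relative to one outcome, the inflation is 6.1/1.7 = 3.6-fold down to 3.3/1.7 = 1.9-fold for four scales, and 12.7/1.7 = 7.5-fold down to 4.8/1.7 = 2.8-fold for ten. Both tables cover one visit, so they leave out any choice among the three follow-up visits. The split-mixed ANOVA was not simulated.

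**Step 3. What the 90% covers.** The value f = 0.40 fixes the spread of the three means but not their pattern, so the patterns below are assumptions.

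- Two groups equal, one apart by d: f = d√2/3, so d = 0.40 × 3/√2 = 0.849 SD. A single Tukey laser-versus-control comparison in which the two groups truly differ then has about 78% power at N = 84.
- Means evenly spaced, control at one end: the gap is 0.40/√(2/3) = 0.490 SD. Power is about 30% for the arm nearer to control and about 89% for the farther arm.

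The chance that at least one laser arm beats control (significant F, then Tukey) is about 89% if both arms work equally, 78% if only one works, and 89% if the means are evenly spaced. A pooled laser-versus-control contrast, two-sided at 5%, has standard error √(1/28 + 1/56) = 0.231 SD. Its power is about 95% if both arms work equally (difference 0.849 SD) and about 44% if only one works (difference 0.849/2 = 0.424 SD).

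**The case against.** The best defence is that the sample-size paragraph already implies the primary analysis: one outcome, one visit, the full 5%, and an N that matches the three-group F test exactly. This stands in part. A reader might infer that the trial has no target at all, and the documents do not support that. The target is visible but is neither labelled nor linked to H1, and the methods section leaves the deciding test open.

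A second objection is that the larger error rates do not measure false efficacy claims. This is correct. A reader might take 36% or 17% as the chance of wrongly declaring laser effective. Those figures count any three-group difference, including laser worse than control, or the two laser schedules differing with neither better than control. On the directional yardstick the rates are about one third as large, and for four scales they are close to 5% or below it at correlations of 0.5 and above.

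Third, the plan does not say that each outcome will be tested at 5%, or that the methods apply to every listed outcome. That is the natural reading of a section that excludes none, so the rates are conditional on it.

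Fourth, ANCOVA is not in the plan, and the contrast that supports H1 is for the investigators to choose. Both points are accepted in the fix.

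**Conclusion.** The point holds as a missing designation. The sizing implies SPADI at month 6, but nothing in the plan makes it the deciding outcome, names the deciding test, or prevents H1 from resting on another of the ten outcomes. If each is tested at 5% at one visit, with correlation assumed between 0.3 and 0.9, a false three-group difference somewhere has a chance of about 17-10% (four scales) or 36-13% (ten outcomes), against 5%. A false finding that laser is better than control has a chance of about 6-3% or 13-5%, against about 1.7%. The absence of the designation is certain. The sizes depend on the assumed correlations and on the testing rule just described.

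N = 84 is not wrong for f = 0.40. The 90% is simply not the power of a single laser-versus-control comparison, and the 78% and 30% figures illustrate this under assumed patterns of means. The plan should be corrected, but the design itself does not have to change.

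**What to change.** Add to Statistical & Analytical Methods:

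> The primary outcome is SPADI at month 6. The primary test is the three-group comparison at the 5% level, adjusted for month-0 SPADI (ANCOVA). If it is significant, pairwise comparisons follow (Tukey, or Games-Howell if variances are unequal); 5 versus 10 sessions is secondary. All other outcomes and visits, including the split-mixed ANOVA, are secondary and reported as estimates with confidence intervals; within-group changes are descriptive.

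The investigators should also state in advance which laser-versus-control result supports H1. Examples are at least one laser arm better than control, or the pooled laser arms against control. Step 3 of the working shows the trade-off: the pooled contrast gains power if both schedules work and loses much of it if only one does.

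The month-0 covariate is a free gain in precision and not the correction of an error. The designation works equally well with the planned one-way ANOVA. Games-Howell is defined for unadjusted means, so if ANCOVA is adopted the plan should say which means the pairwise step uses when variances are unequal.

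In Sample Size, state that the 90% power applies to the three-group test and that a single laser-versus-control comparison may have less.

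The change adds no patients, visits or measurements, since month-0 SPADI is already collected. Its price is that other outcomes can no longer carry the efficacy claim alone, and that the stated power looks less favourable for a single laser arm.

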Patients diagnosed with partial supraspinatus tear on working days will be evaluated in the ftr outpatient clinic and suitable patients will be included in the study. Demographic information of the patients will be recorded. Consent will be obtained from the patients on the same day. Patients randomized to 3 groups will be included in the treatment protocol prescribed for each group at 0, 1, 3 and 6 month will be evaluated with VAS, shoulder

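### Month-0 scores are collected in every arm, but the plan names no baseline covariate and does not say how month 0 is used or which term is the between-arm test; precision is lost, validity is not

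*Combined protocol and SAP*

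**What the plan says.** The Study Design section lists the assessments for all groups, ending with "constant score at 0th month, 1st month, 3rd and 6th months". The visit description in the same chapter repeats that patients "at 0, 1, 3 and 6 month will be evaluated with VAS, shoulder" pain and disability index, QuickDASH, Constant score and range of motion. A pre-treatment value of every outcome is therefore planned for every patient.

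Statistical & Analytical Methods states: "Analysis of variance (ANOVA) and split-mixed ANOVA will be used in the analysis of within-group changes and in repeated measures of significance". The sentence goes on to mention differences between the groups, and the next one names Tukey and Games-Howell as post-hoc tests. Neither document section mentions ANCOVA, a covariate or baseline adjustment. Three things are left open: which visits are levels of the time factor, whether the arms are compared through the group main effect or the group-by-time interaction, and whether the plain ANOVA uses raw scores or changes.

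The Sample Size paragraph refers to SPADI "for the 6th month before and after the treatment" and says "it was predicted that a high level of effect size would be obtained between the groups (f=0.40"), with "90% power, and type 1 error level: 5"%, giving 84 patients, raised to 90 for losses.

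**The concern.** A patient's score before treatment usually predicts the score afterwards. If it is in the model, the part of the month-6 variance that it explains leaves the error term, and chance differences between arms at entry are allowed for. If it is not in the model, that information is lost although it has been collected.

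The arms have 30 patients each, and no stratification by baseline severity is described. The secondary purpose compares 5 with 10 sessions, two active arms between which a smaller difference is plausible, so precision matters most there.

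The open wording adds to this. Someone analysing the trial could report a single-visit ANOVA, an ANOVA of changes, a group main effect or an interaction, and each would fit the text. These tests answer different questions and have different power.

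**Working it through.** **Inputs from the documents.** Three arms of 30 (Study Design); f=0.40, power 90%, alpha 5%, N=84 before losses (Sample Size); visits at months 0, 1, 3 and 6.

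**Assumptions.** The correlation rho between month-0 and month-6 scores is not in the documents, so a range is shown. Variances are equal across arms and visits. For the split-mixed ANOVA, rho is common to all pairs of visits.

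**1. The plan's own figure.** One-way ANOVA with k=3, noncentrality N·f², df (2, N−3). At N=84: 84 × 0.16 = 13.44, df (2, 81), power 90.7%. The smallest N reaching 90% is 83, or 84 in equal groups. The stated 84 is reproduced, and it corresponds to a one-way ANOVA without a covariate. At N=90 power is 92.6%.

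**2. Three ways to analyse month 6.** Relative to the raw month-6 score, the error variance is multiplied by:
- single-visit ANOVA: 1
- ANOVA of changes from month 0: 2(1−rho)
- ANCOVA on month 0: 1−rho²

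Since 2(1−rho) − (1−rho²) = (1−rho)², the change score has the larger variance for any rho below 1. It is also worse than ignoring baseline when rho is below 0.5. ANCOVA uses f² = 0.16/(1−rho²) and loses one error df.

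| rho | ANCOVA factor | ANCOVA power, N=84 | N for 90% with ANCOVA | Change factor | Change power, N=84 |
|---|---|---|---|---|---|
| 0.3 | 0.91 | 93.2% | 78 | 1.40 | 78.3% |
| 0.5 | 0.75 | 96.9% | 63 | 1.00 | 90.7% |
| 0.7 | 0.51 | 99.7% | 45 | 0.60 | 99.0% |

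The unadjusted comparison is 90.7% and N=84. At rho 0.2 the ANCOVA factor is 0.96 and power is about 92%. ANCOVA standard errors are the square root of the factor: about 5%, 13% and 29% smaller at rho 0.3, 0.5 and 0.7.

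**3. Split-mixed ANOVA with month 0 as a level of time.** The group main effect is a comparison of four-visit means. A difference constant from month 1 but absent at month 0 shrinks to 3/4, and the mean has variance (1+3·rho)/4. At rho 0.5: f² = 0.75² × 0.16 / 0.625 = 0.144, so f=0.379 and power is 87.3%. The group-by-time interaction has (3−1)(4−1) = 6 numerator df and takes month 0 as part of the contrast, so it is not diluted in this way. Power at N=84 and rho 0.5:

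| Effect pattern (f=0.40 at month 6) | Group main effect | Interaction |
|---|---|---|
| Full from month 1 | 87.3% | 93.6% |
| Linear growth to month 6 | 37.8% | 85.1% |
| Month 6 only | 15.9% | 93.6% |

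The two low main-effect figures also reflect averaging over months 1 and 3, not month 0 alone. A significant interaction says that the time profiles differ somewhere; it does not isolate month 6.

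**4. Chance imbalance.** The baseline difference between two arms of 30 has SD √(2/30) = 0.26 in SD units. It carries into an unadjusted month-6 difference at about rho times that: 0.08 to 0.18 SD for rho 0.3 to 0.7.

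**5. Would restricting the split-mixed ANOVA to months 1, 3 and 6, with month 0 as covariate, do as well?** Not reliably. At rho 0.5 its adjusted group effect has about 80% power under linear growth and 36% if the effect appears only at month 6. The month-6 ANCOVA has 96.9% in both cases, because only the month-6 difference enters it.

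**The case against.** The plan is valid as it stands. An unadjusted month-6 ANOVA already has 90.7% power at the plan's f, and chance baseline imbalance is variance already counted in that power, not bias. This stands, and it limits the point to efficiency and specification.

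A reader might infer that month 0 enters only as one more repeated visit. The text does not say so. It refers to within-group changes and to differences between groups, so an ANOVA of changes, which does use each patient's month-0 value, is a natural reading. No reading, however, makes month 0 a covariate.

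A reader might also infer that the planned test is diluted by a pre-treatment visit. That holds only if month 0 is a level of time and the group main effect is the test. The interaction is not diluted, and the plan chooses neither.

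The gain depends on a correlation that the documents do not give. Entry requires VAS above 4, which truncates baseline VAS and may lower its correlation with later scores, so a useful gain is not assured for every outcome. This stands too; at low rho the gain is small.

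Finally, Games-Howell works on raw group means with separate variances, so a move to adjusted means must name a replacement. The fix does so.

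**Conclusion.** The point holds as a loss of precision together with an unspecified between-arm test. The plan collects month 0 on every outcome, names no covariate, and does not say how month 0 is used. Under the plan's f=0.40 with 84 analysed, ANCOVA raises month-6 power from 90.7% to 93.2%, 96.9% or 99.7% at rho 0.3, 0.5 or 0.7, and to about 92% at rho 0.2. An ANOVA of changes, also compatible with the wording, would fall to 78.3% at rho 0.3. These figures rest on the assumed rho and equal variances; the split-mixed figures also need a common correlation between visits. Nothing here shows inflated type I error or a wrong sample size. It should be changed because the gain needs no new data, but the trial is not invalid without it.

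**What to change.** In Statistical & Analytical Methods:

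- Make the between-arm comparison at month 6 an ANCOVA, with arm as factor and the month-0 value of the same outcome as covariate. Do the same at months 1 and 3 as supportive analyses.
- Run the three pairwise comparisons on the baseline-adjusted means with a named multiplicity adjustment that is available for adjusted means, for example Sidak or Bonferroni, in place of Tukey and Games-Howell for these contrasts.
- Keep the split-mixed ANOVA as a supportive description of the time course, and state which visits are levels of time.
- Keep N=90. Do not reduce it on the strength of an assumed correlation.

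The cost is a change of wording, one error degree of freedom per single-visit model, and the replacement of the post-hoc tests for these contrasts. No additional data are needed.
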